5. ADVERSE EVENTS

5.1. Definitions

Adverse Event (AE): any untoward medical occurrence in a patient or clinical study subject.

Serious Adverse Event (SAE): any untoward and unexpected medical occurrence or effect that:

- **Results in death**
- **Is life-threatening** – *refers to an event in which the subject was at risk of death at the time of the event; it does not refer to an event which hypothetically might have caused death if it were more severe*
- **Requires hospitalisation, or prolongation of existing inpatients' hospitalisation**
- **Results in persistent or significant disability or incapacity**
- **Is a congenital anomaly or birth defect**

Medical judgement should be exercised in deciding whether an AE is serious in other situations. Important AEs that are not immediately life-threatening or do not result in death or hospitalisation but may jeopardise the subject or may require intervention to prevent one of the other outcomes listed in the definition above, should also be considered serious.

5.2. Reporting procedures

All adverse events should be reported. Depending on the nature of the event the reporting procedures below should be followed. Any questions concerning adverse event reporting should be directed to the Chief Investigator in the first instance.

5.2.1. Non-serious AEs

All such events, whether expected or not, should be recorded.

5.2.2. Serious AEs

An SAE form should be completed and faxed to the Chief Investigator within 24 hours. However, recurrence of or death related to neurocardiogenic syncope, and hospitalisations for elective treatment of a pre-existing condition do not need reporting as SAEs.

All SAEs should be reported to the to the **[Placeholder for Ethics Committee]** where in the opinion of the Chief Investigator, the event was:

- 'related', i.e. resulted from the administration of any of the research procedures; and
- 'unexpected', i.e. an event that is not listed in the protocol as an expected occurrence

Reports of related and unexpected SAEs should be submitted within 15 days of the Chief Investigator becoming aware of the event, using the NRES SAE form for non-IMP studies. The Chief Investigator must also notify the Sponsor of all related and unexpected SAEs.

Local investigators should report any SAEs as required by their Local Research Ethics Committee, Sponsor and/or Research & Development Office.

Contact details for reporting SAEs:

Please send SAE forms to: [name]: [contact], [name]: [contact] and Imperial research governance and integrity [contact]

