4.2. Inclusion criteria

Patients with atrial Fibrillation that have been put forward for an ablation or DCCV based on clinical grounds.

- Suitable candidate for catheter mapping/ablation or direct current cardioversion for atrial fibrillation
- Eighteen (18) to eighty-five (85) years of age
- Able to give informed consent

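### The SAE rules exempt deaths related to neurocardiogenic syncope, against the protocol's own definition of serious, and use *unexpected* in two places that do not fit together

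*Combined protocol and SAP*

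**What the plan says.** The safety rules are in Section 5 of the protocol.

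- **Section 5.1 (Definitions)** describes an SAE as "any untoward and unexpected medical occurrence or effect that" meets one of the listed criteria. The first criterion is "Results in death". A further paragraph lets medical judgement extend seriousness to other important events.
- **Section 5.2 (Reporting procedures)** opens: "All adverse events should be reported. Depending on the nature of the event the reporting procedures below should be followed". It sets no time limit.
- **Section 5.2.1** asks for events to be recorded whether expected or not, but its heading confines it to non-serious events.
- **Section 5.2.2 (Serious AEs)** sets the urgent route: "An SAE form should be completed and faxed to the Chief Investigator within 24 hours". It then makes an exception: "recurrence of or death related to neurocardiogenic syncope, and hospitalisations for elective treatment of a pre-existing condition do not need reporting as SAEs". Finally it selects which SAEs go to the ethics committee (within 15 days) and to the sponsor: those judged both related and unexpected. Unexpected is explained there as "an event that is not listed in the protocol as an expected occurrence".

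The population in Section 4.2 is "Patients with atrial Fibrillation that have been put forward for an ablation or DCCV based on clinical grounds". The available text contains no list of expected occurrences.

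**The concern.** There are two separate faults.

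The first is the syncope exemption. It takes a class of deaths out of SAE reporting, although the definition a page earlier treats death as serious. No reason is given, and the condition has no other role in the protocol. Under Section 3.2, patients have general anaesthesia or sedation, shocks and, in the ablation group, adenosine given to produce transient AV block. Whether a collapse in that setting was syncope-related is a matter of attribution. Under the current wording, that attribution decides whether a death is reported as an SAE.

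The second is the placing of *unexpected*. Seriousness normally decides whether an event is an SAE, and expectedness decides who else must be told. Here expectedness is used at both stages, but is explained only at the second. Depending on how the word is read in 5.1, the same complication can be inside or outside the 24-hour rule. At stake are prompt notice to the Chief Investigator and consistent classification of serious events.

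**Working it through.** No arithmetic applies: the documents give no adverse event rates, and the point does not depend on alpha, power or sample size. The check sets Sections 5.1 to 5.2.2 side by side and follows example events through them.

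**Step 1: the exemption against the definition.** A death related to neurocardiogenic syncope meets a 5.1 criterion of seriousness. Section 5.2.2 says it need not be reported as an SAE. This holds whatever *unexpected* means. What remains is the untimed opening sentence of 5.2; 5.2.1 does not apply, because a death is not a non-serious event.

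**Step 2: the double use of *unexpected*.** Write S for meeting a seriousness criterion, U for unexpected and R for related.

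- SAE under 5.1 = S and U.
- Onward report under 5.2.2 = SAE and R and U = (S and U) and R and U = S and U and R = SAE and R.

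If U means the same thing in both places, the second U does no work. It has a function only if the word differs in meaning between the sections, or was not meant to be part of the SAE definition. The two sections therefore do not fit together as written.

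**Step 3: one event, different readings.** Take a serious but recognised complication of a study procedure.

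| Reading of *unexpected* in 5.1 | SAE under 5.1? | 24-hour form (5.2.2)? | Covered by 5.2.1? | What remains |
|---|---|---|---|---|
| Ordinary meaning (not foreseeable) | No | No | No, the event is serious | Untimed statement in 5.2 |
| Meaning given in 5.2.2, nothing listed (current text) | Yes | Yes | Not needed | Full SAE route |
| Meaning given in 5.2.2, after a list naming this event is added and 5.1 is left alone | No | No | No, the event is serious | Untimed statement in 5.2 |
| Expectedness removed from 5.1 | Yes | Yes | Not needed | Full SAE route; related and unexpected events also go to ethics and sponsor |

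Rows 1 and 2 give opposite answers from the same current text. Row 3 shows that supplying the missing list alone would turn a possible gap into a definite one.

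**Step 4: the missing list.** With nothing listed, every SAE counts as unexpected under 5.2.2, so every related SAE goes to the ethics committee and sponsor. The direction is over-reporting, and the rule is at least uniform.

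**The case against.** The strongest reply is that the protocol explains *unexpected* in only one place, Section 5.2.2, and that explanation depends on a list that does not exist. Carried back into 5.1, it makes every event unexpected, so no serious event is lost from the 24-hour route. This stands. A reader might infer that serious expected procedural events do escape urgent reporting and that the SAE count will be too low. The documents do not support that as a certainty: it follows only if 5.1 uses the word in its ordinary sense, which the text neither says nor rules out. The reply does not remove the conflict, since 5.1 does not point to the 5.2.2 explanation and the later test remains redundant. Nor does it touch the syncope exemption.

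A second reply is that 5.2 requires all adverse events to be reported. That is true, and it means events are not lost altogether. But the sentence has no time limit and defers to the procedures beneath it. Section 5.2.1 should not be counted as a further safeguard, because it covers non-serious events only.

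A third reply is that syncope-related deaths may never occur in this cohort, and that SAE counts are not among the outcome measures in Section 3.1. Both are fair limits on the practical effect. Neither gives a reason for exempting a death.

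Two further inferences should be resisted. A reader might conclude that the exemption was copied from another study's protocol. The absence of syncope elsewhere makes that plausible, but the documents do not state its origin and the contradiction does not depend on it. A reader might also say that the missing list leaves the ethics test unworkable. As Step 4 shows, it works but catches more than intended; this is missing detail rather than a reporting gap.

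**Conclusion.** The syncope exemption is a plain contradiction: Section 5.2.2 releases from SAE reporting a kind of death that Section 5.1 classes as serious, for a condition otherwise absent from the available text. That conclusion rests on no assumption about how *unexpected* is read.

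The double use of *unexpected* is a real inconsistency, but its consequence is conditional. On the ordinary meaning, a serious recognised complication could fall between 5.2.1 and 5.2.2 and be left with an untimed duty to report. On the 5.2.2 meaning, none would. The size is therefore a risk of inconsistent classification, not a demonstrated shortfall, and no number can be put on it because no event rates are given.

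The effect is confined to safety reporting. The finding assumes that the removed pages contain neither a list of expected events nor another mention of neurocardiogenic syncope. The rules should be corrected, since they govern prompt notice of serious harm and the correction is short.

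**What to change.** Make these changes together in one amendment:

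1. In Section 5.2.2, delete the exemption for recurrence of, or death from, neurocardiogenic syncope. The exemption for planned admissions is not in question here.
2. In Section 5.1, delete the words that make an SAE unexpected, so that seriousness alone defines it and the 24-hour form applies to every SAE not otherwise exempted.
3. In Section 5.2.2, keep related and unexpected solely as the test for onward reporting to the ethics committee and sponsor.
4. If a list of expected occurrences is added later, state that it bears only on that onward test and does not narrow the 24-hour rule. Do not add it while 5.1 stands unchanged.

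The drafting cost is two deletions and a clarifying sentence. The running cost is some additional SAE forms. For example, an unplanned admission for recurrent AF would clearly be an SAE; the protocol plans 300 patients and cites ablation success of only 50% in persistent AF. It gives no admission rate, so the number of extra forms cannot be derived and should not be assumed to be small.

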5.2.3. Incidental Findings

In the event an incidental finding is uncovered during the study, the relevant clinical team will be immediately notified. We will also inform the patient's GP, with the patient's permission (relevant clause is present on the informed consent form).

6. ASSESSMENT AND FOLLOW-UP

Patients undergoing AF ablation and the 252 lead ECG protocol will be provided with an AliveCor device to use up to once per day and when they have symptoms to accurately monitor for recurrence of AF. They will also be asked to complete symptom score (36-Item Short Form Survey Instrument (SF-36) and Atrial Fibrillation Effect on Quality-of-life (AFEQT)) questionnaires up to once per month. They will have Holter monitoring and clinical follow up in line with routine clinical care.

Patients undergoing DCCV will be followed as per routine clinical care for 1 year.

The end of study is when the last patient has completed their last follow up visit.

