3.1. Study outcome measures

We will classify patients into electrophenotypes based on the invasive and non-invasive data collected. The primary outcome measure will be freedom from AF. Secondary outcome measures will be AF burden and quality of life.

[figure not shown]

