Patients undergoing AF ablation will be provided with an AliveCor device to use up to once per day and when they have symptoms to accurately monitor for recurrence of AF. They will also have holter monitoring and clinical follow up in line with routine clinical care. Patient's will be asked to complete symptom score/quality of life questionnaires up to once per month during follow up.

Patients undergoing DCCV will be followed as per routine clinical care.

Study participation will conclude after 300 patients have been recruited. Patients will be able to leave the study at any time they wish; they need only inform the research team.

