We will look for differences in lipid metabolite levels, miRNA and protein expression between the electrophenotype groups, which may serve as biomarkers to non-invasively distinguish between these groups. I will analyse human serum using DNA barcode technology integrated with a nanopore platform to measure levels of these circulating miRNAs and proteins. Machine learning has been used effectively in proteomic studies (30). I aim to apply the biomarker data with electrical and imaging data using unsupervised machine learning to identify clinically relevant clusters (phenotypes).

Developing non-invasive methods to classify AF electrophenotype

Using simultaneously collected 252 lead ECG and intracardiac data, together with CMR LA fibrosis data, the surface ECG and biomarkers, I will develop tools to non-invasively classify AF electrophenotype.

Using the intracardiac data as the gold standard, I will continue to develop tools to determine the degree of global fibrillation organisation from surface ECGs, using band-power feature analysis and machine learning techniques. 252 lead ECG-derived biatrial maps in atrial fibrillation will then be analysed using both established (dominant frequency, phase mapping and Shannon entropy) and the novel (ML based analysis, including unsupervised machine learning) to further stratify patients into a spectrum of organised to disorganised electrophenotypes. Simultaneous

intracardiac and 252 lead ECG recordings will also allow further validation of 252 lead ECG in atrial fibrillation. I will use CMR data to correlate electrophenotype with anatomical data. LA fibrosis will be categorised by both degree and distribution of fibrosis and correlated with both intracardiac and non-invasively acquired electroanatomical data using linear regression models and ML. Invasive and non-invasive parameters will be combined and correlated with AF recurrence to create a tool using only non-invasive data to determine a patient-specific electrophenotype.

Outcomes

Freedom from AF, AF burden and quality of life outcome data will be correlated with electrophenotype groups (as defined by the above analyses) to investigate if certain groups benefit more from ablation than others.

Sample size is based on collecting sufficient data to detect differences in electrophenotypes using biomarkers and ECG parameters.

Data will be analysed by the chief investigator and the research team at the National Heart and Lung Institute, Imperial College London.

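### Quality of life is collected repeatedly on two instruments, but the plan names no main score, fixed months, pre-procedure form or method for repeated returns

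*Combined protocol and SAP*

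**What the plan says.** Section 3.1 gives quality of life its role: "Secondary outcome measures will be AF burden and quality of life". No instrument or score is named there.

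Section 6 names two instruments and a frequency: the SF-36 and "Atrial Fibrillation Effect on Quality-of-life (AFEQT)) questionnaires up to once per month". Section 3.2 says the same without naming them: "symptom score/quality of life questionnaires up to once per month during follow up". Neither section says which instrument is the main one, sets particular months or a minimum number of forms, or schedules a form before the procedure.

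The analysis is one sentence under Outcomes in section 7: "Freedom from AF, AF burden and quality of life outcome data will be correlated with electrophenotype groups". Its stated purpose is "to investigate if certain groups benefit more from ablation than others". The only regression method named in section 7 concerns left atrial fibrosis, which is to be "correlated with both intracardiac and non-invasively acquired electroanatomical data using linear regression models and ML". It is not applied to quality of life.

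Two points bear on size. Section 3.2 asks ablation patients generally to complete the forms, while section 6 limits the request to ablation patients who are also in the 252 lead ECG protocol. Section 3.2 puts that ECG subgroup at 50-100 patients, including some who have cardioversion. The documents give 1 year of follow-up for cardioversion patients and no length for ablation patients.

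**The concern.** A correlation with group membership needs either one value per patient or a rule for handling several. The plan has several values on two instruments and gives no rule. Three routes are open: pick one month, stack all forms as if they were independent, or average each patient's forms. The first discards information. The second understates the standard error. The third mixes different stages of recovery if groups return forms at different times.

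There is also a question of meaning. Section 7 asks which groups gain more from ablation. Without a pre-procedure score, a difference that existed before ablation would be read as a difference in gain.

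At stake is a secondary comparison meant to say which electrophenotypes do better after ablation, in what may be a small set of patients.

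**Working it through.** **No figure to reproduce.** The plan gives no alpha, power, effect size or standard deviation for quality of life. Section 7 bases the sample size on biomarkers and ECG parameters. Everything below therefore rests on assumptions: two equal groups, two-sided 5% tests, m forms per patient and a constant within-patient correlation ρ.

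**1. One month against the mean of m months.** The variance of the mean relative to a single score is (1 + (m − 1)ρ)/m. For m = 12:
- ρ = 0.5: (1 + 5.5)/12 = 0.54, so one month needs 12/6.5 = 1.85 times the patients.
- ρ = 0.8: (1 + 8.8)/12 = 0.82, so one month needs 12/9.8 = 1.22 times the patients.

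To detect 0.4 SD with 80% power, a single month needs 99 per group. The mean of 12 needs 54 at ρ = 0.5 and 72 at ρ = 0.7. With 50 per group, power is 0.52 for a single month, against 0.78 and 0.65 for the mean.

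**2. Forms stacked as independent.** The false-positive rate is 2(1 − Φ(1.96/√D)), with D = 1 + (m − 1)ρ.

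| Forms | ρ | D | False-positive rate |
|---|---|---|---|
| 3 | 0.5 | 2.0 | 17% |
| 3 | 0.8 | 2.6 | 22% |
| 6 | 0.5 | 3.5 | 30% |
| 6 | 0.8 | 5.0 | 38% |
| 12 | 0.5 | 6.5 | 44% |
| 12 | 0.8 | 9.8 | 53% |

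**3. Per-patient mean, by simulation with no true difference.** In the first scenario there were 50 per group, 12 months and about half the forms returned.
- Random return: the mean gave 3-7% false positives and a mixed model 5-6% (ρ 0.3 to 0.7).
- One group returning earlier: that group returned 80% of forms in months 1-6 and 20% afterwards, and the other returned 50% throughout. Both improved by 0.06 SD a month, with ρ = 0.5. The expected mean month of return is 0.8 × 3.5 + 0.2 × 9.5 = 4.7 in one group and 6.5 in the other. The gap of 1.8 months × 0.06 gives a spurious difference of about 0.11 SD (0.10 simulated). False positives were 9% for the mean, 7% for the mixed model and 42% for stacked forms.

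A second scenario had 30 per group, about half the forms returned, a 1 SD recovery trend and one group returning earlier. False positives were 10-12% for the mean, about 5% for the mixed model and 42-44% for stacked forms. At a true difference of 0.5 SD, power was 0.60-0.71 for the model against 0.36-0.45 for the mean. That power gap applies when the timing bias opposes the true difference. When the two point the same way, the mean exaggerates the difference instead.

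**4. Where the mixed model fails.** Suppose only one group returns more forms when its quality of life is low. The model's false-positive rate was then 76%, 42% and 21% at ρ = 0.3, 0.5 and 0.7, with bias of −0.34, −0.27 and −0.18 SD. When both groups behaved this way to the same degree (ρ = 0.5), the rate was 4%.

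The simulations used 250-300 runs per setting in the first scenario and in point 4, so rates carry a Monte Carlo error of about 1-3 percentage points. The model in those runs had a patient random intercept, month and group. It had no baseline or group-by-month term.

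**The case against.** The strongest reply is that section 7 proposes none of the harmful analyses. Correlation is a loose word, and a sensible analyst could take one mean per patient, which uses every form and holds its error rate when return is random. This stands for random return. It does not answer differential timing, and the plan does not commit to that summary.

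Three stronger readings are tempting, and the documents do not support them.
- A reader might infer that patients choose their own months. The text sets only a maximum frequency and does not say who fixes the dates.
- A reader might infer that all 2 × 12 = 24 month-by-instrument comparisons will be tested. With two groups of 50 and a correlation of 0.7 between instruments, the chance of at least one p < 0.05 would be about 53% falling to 28% as ρ rises from 0.5 to 0.8. No passage proposes this, and it assumes complete returns over a follow-up the plan does not state for ablation patients.
- A reader might infer that a mixed model alone cures the problem. Point 4 of the working shows that it does not when symptom-driven return differs between groups.

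It is also fair to say that the outcome is secondary, the study is exploratory, and the plan sets no significance threshold. That limits the consequence but does not remove the gap.

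**Conclusion.** The concern holds as a gap in specification for which a better and inexpensive method exists. The documents establish two instruments, a frequency ceiling, no scheduled pre-procedure form, and an analysis sentence that ignores repeated returns and time since the procedure.

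The size depends on the route taken. The loss of precision and the stacking error follow from standard formulae once ρ and the number of forms are assumed. The timing bias is scenario-dependent, and it is small or absent if forms come back at random. The number of groups, their sizes, ρ, 12 months of follow-up and the return patterns are all assumptions. If section 6 governs who completes forms, 50 per group is the most that two equal groups could contain.

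The missing baseline matters whichever route is taken, because the question asked is about gain from ablation. Importance is moderate: the plan should be changed, but the primary outcome is unaffected.

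**What to change.** In section 6, ask for the forms at fixed months, including one before the procedure, and reconcile sections 3.2 and 6 on which ablation patients complete them.

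In section 7:
- Name one main score, for example the AFEQT overall score, with SF-36 supportive.
- Analyse all returns in a linear mixed model with a patient random effect, baseline score, month since procedure, electrophenotype and electrophenotype-by-month.
- Report the baseline-adjusted difference averaged over follow-up as the single main estimate.
- Report the number of returns per patient by electrophenotype.
- Add a sensitivity analysis for return that depends on current symptoms.

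The cost is some plan wording, a standard model, one added pre-procedure form and a questionnaire calendar. SF-36 loses equal standing. Patients already past their procedure cannot supply a true baseline, so the earlier the change is made, the more it is worth.
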